### **6.1. Study Design**

This is a prospective, multi-center, controlled, randomized study in which a non-inferiority (NI) design will be employed to evaluate the clinical effectiveness of Mirasol (MIR)-treated versus Conventional (CONTROL) apheresis (Aph) platelets (PLTs) in subjects with hematologic malignancies with hypoproliferative thrombocytopenia expected to have PLT count(s)  $\leq 10,000/\mu\text{L}$  and requiring  $\geq 2$  PLT transfusions. Subjects will be randomized by a ratio of 1:1 (MIRASOL vs CONTROL group) using a permuted-block schedule stratified by investigational site and type of treatment (allogeneic transplant vs autologous transplant vs chemotherapy). Randomization will occur as close to the initiation of the first study transfusion as possible, within five (5) days prior to the anticipated initiation of PLT transfusion(s).

Subject participation will be for up to eighty-one 81 days; a 14-day screening period, a 28-day treatment period, and a 28-day follow-up period. Study Day (also referred to in this document as ‘Day’) 0 of the treatment period is defined as the day of the first study transfusion following randomization. The primary, secondary, and exploratory endpoints will be based on data captured during the treatment period (Day 0 to transfusion independence or Day 28, whichever comes first). Transfusion independence is defined as ten (10) days without a PLT transfusion prior to date of last contact or Day 28 whichever is earlier. The date of transfusion independence will be the 10th day without a PLT transfusion.

Daily bleeding assessments assess bleeding for the previous day. The first bleeding assessment to be used for analysis of primary and secondary endpoints etc., will be collected on Study Day 1 which assesses bleeding at Study Day 0. Bleeding assessments are planned to occur on Study Days 0-27 and at the post transfusion follow-up visit. Consequently, there will be a maximum of 28 bleeding assessment days used for analysis. The bleeding assessments to be included in analysis are greyed out the in schematic below.

Study Day	0 (first transfusion day)*	1	2	3	4	5	6	27	Post transfusion/ Follow-up (in some cases Study Day 28)
Day bleeding assessed (24 hours previous to Study Day)	-1	0	1	2	3	4	5	26	27 + 2-day window allowed for visit

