#### **8.4.4. Treatment Emergent Adverse Events**

The following will be displayed.

- Overall TEAEs
- Platelet Transfusion Related TEAEs
- Medical Device Related TEAEs
- TEAEs by maximum severity
- SAEs
- UADEs
- Pulmonary events
  - Subjects on assisted ventilation
- TEAEs causing discontinuation from the study
- All-cause mortality
- Death due to bleeding as the primary or contributory cause of mortality

All TEAEs/SAEs identified during the reporting period (i.e. from initial post randomization platelet transfusion through seventy-two (72) hours following the transfusion end time of the last on-protocol PLT transfusion; for deaths including deaths due to bleeding through thirty (30) days following the transfusion end time of the last on-protocol PLT transfusion) will be followed until resolution, stabilization, or the end of subject's study participation, whichever is first.

Treatment Emergent Adverse Events are defined as those that occur during or following the first post-randomization PLT transfusion. The AE start date and time and transfusion start date and time of the first study transfusion will be used to identify TEAEs. The transfusion end time of the subject's final study transfusion will be used to identify the end of the 72-hour reporting period (or 30 days for deaths). AEs with missing/impartial start date and or time will be considered to be treatment emergent.

Treatment Emergent Serious Adverse Events (TESAEs) are defined as TEAEs marked serious by the investigator. Transfusion-related TEAEs are described through the reporting of TEAEs identified as related to the study treatment or those related to the medical device.

Unanticipated Adverse Device Effects are any serious adverse effect on health or safety or any life threatening problem or death caused by, or associated with, a device, if that effect, problem, or death was not previously identified in nature, severity, or degree of incidence in the investigational plan or application, or any other unanticipated serious problem associated with a device that relates to the rights, safety, or welfare of subjects

Unanticipated Adverse Device Effects will be identified as treatment emergent adverse events reported by the investigator as serious, unanticipated, at least possibly related to study device or at least possibly related to study treatment.

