Medical Dictionary for Regulatory Activities preferred terms in the associated SOC and Standard Medical Queries (SMQs) will be used to categorize TEAEs of “Pulmonary events” and additionally those pulmonary events requiring assisted ventilation as defined by the investigator.

Subject related TEAE counts will be summarized using frequencies and percentages. A subject will only be counted once per category of summarization (i.e. if a subject has multiple TEAEs, the subject will only be counted once in the overall ‘Any TEAE’ row but will be counted in each row for specific TEAEs). Event counts will be summarized using frequencies of events by treatment group.

A summary of TEAEs will be generated summarizing the number of TEAEs, TESAEs, unanticipated TESAEs, and UADEs. The number and percent of subjects with at least one TEAE, TESA, TEAE related to study treatment, TEAE related to medical device(s), and TEAEs of pulmonary events and additionally those requiring assisted ventilation will also be included. The number of TEAEs by severity, relationship to study treatment (platelet transfusion) and relationship to the medical device, will be included.

Summary tables by SOC and PT will be reported for TEAEs, TESAEs, unanticipated TESAEs, UADEs, and Pulmonary related TEAEs as well as those pulmonary events requiring assisted ventilation. The number and percent of subjects with at least one event will be presented overall and, at most, once per SOC and PT.

All TEAEs will be listed by treatment group and subject. There will be a separate listing of TESAEs by treatment group and subject.

The timeframe for reporting death as part of AEs and death as a safety endpoint are different. The timeframe for reporting death as an AE is from randomization through thirty (30) days following the last per protocol PLT transfusion, where the timeframe for reporting death as a safety endpoint of death is through Day 56. The number of deaths through thirty (30) days following the last on-protocol PLT transfusion will be summarized by relationship to study treatment (PLT transfusion) and by relationship to medical device(s). The total number of deaths through Day 56 will be reported.

All deaths will be listed by treatment group and subject. This listing will include the investigator assessment of cause of death.

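### The default for missing adverse-event start times has no exception for events whose recorded date already places onset before the first transfusion

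*SAP*

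**What the plan says.** All the relevant text is in SAP section 8.4.4; the document supplied as the protocol carries the same section.

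- Definition: "Treatment Emergent Adverse Events are defined as those that occur during or following the first post-randomization PLT transfusion". It sets a lower bound and no upper bound.
- Data used: "The AE start date and time and transfusion start date and time of the first study transfusion will be used to identify TEAEs".
- Default: "AEs with missing/impartial start date and or time will be considered to be treatment emergent". I read the second word of the pair as meaning partial.
- Reporting period, given separately from the definition: "from initial post randomization platelet transfusion through seventy-two (72) hours following the transfusion end time of the last on-protocol PLT transfusion". A later sentence says that the end time of the subject's "final study transfusion will be used to identify the end of the 72-hour reporting period".

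TEAEs marked serious become TESAEs. UADEs are identified from TEAEs. The pulmonary and assisted-ventilation summaries, the severity and relationship counts, and the tables by system organ class and preferred term also start from TEAEs. Summaries are frequencies and percentages by arm in the Safety Set.

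**The concern.** The default is triggered by a missing time alone, even when the date is complete. It is meant for events whose timing relative to the first transfusion is unknown, but a complete date usually settles that question. As written, two events with the same date before the first transfusion are classified differently according to whether someone wrote down the hour.

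Section 6.1 allows randomization up to five days before the anticipated first transfusion, so there is a stretch of calendar time in which such events could occur. If they are in the database, the literal rule carries them into every table built on the TEAE flag, although the SAP's own definition excludes them.

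**Working it through.** The plan gives no adverse-event rate, no frequency of missing start times and no safety test, so there is no figure to reproduce. The check is a comparison of the definition with the default, case by case. The cases are my examples; Day -3 lies inside the five-day gap that section 6.1 allows.

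| What is recorded about onset | TEAE by the definition? | TEAE under section 8.4.4 as written? | Do they agree? |
|---|---|---|---|
| Day -3, time recorded | No | No (default not used) | Yes |
| Day -3, time missing | No | Yes | **No** |
| Month and year only, that month over before the month of the first transfusion | No | Yes | **No** |
| Day 0, time missing | Cannot be told | Yes | Conservative default, reasonable |
| Nothing recorded | Cannot be told | Yes | Conservative default, reasonable |
| After Day 0, time missing | Yes | Yes | Yes |
| Two weeks after the last transfusion, time recorded | Yes (no upper bound) | Yes (default not used) | Yes |
| Two weeks after the last transfusion, time missing | Yes (no upper bound) | Yes | Yes |

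The conflict is confined to the second and third rows: incomplete records whose known part already places onset before the first transfusion.

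The SAP uses a narrower rule for the same kind of problem in section 7.6. For baseline values, the unknown-time default applies only when the assessment and the first transfusion fall on the same date; otherwise the date decides. Section 8.4.4 lacks that restriction.

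**Can a size be given?** Suppose a share q of subjects in each arm gains a false event in some category, independently of true status. The tabulated risk is then 1 - (1 - p)(1 - q). All values of p and q here are assumptions.

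- True 5% v 10%, q = 2%: 1 - 0.95 × 0.98 = 6.9% and 1 - 0.90 × 0.98 = 11.8%. The ratio goes from 2.00 to 1.71; the difference from 5.0 to 4.9 points.
- True 5% v 10%, q = 5%: 9.75% and 14.5%. Ratio 1.49; difference 4.75 points.
- True 60% v 70%, q = 2%: 60.8% and 70.6%. The ratio goes from 1.167 to 1.161; the difference from 10.0 to 9.8 points.
- q = 0: nothing changes.

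The difference shrinks only by the factor (1 - q). The ratio moves noticeably only for uncommon categories. Since q is not in the documents and may be zero, these figures show a direction under equal misclassification and not the size of an effect in this trial.

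**The case against.** The strongest reply is that the rule may never bite. The reporting period opens at the first post-randomization transfusion. The only stated capture before that concerns deaths: "The timeframe for reporting death as an AE is from randomization through thirty (30) days following the last per protocol PLT transfusion". A subject who dies before any platelet transfusion is not in the Safety Set, so that capture cannot create a false TEAE. Collection of non-fatal events before transfusion is a matter for the Clinical Investigation Plan, which is not among the documents. Counting events of uncertain timing as treatment emergent is also a usual conservative choice, and every TEAE is listed by subject. All of this stands, and it limits the severity. It does not remove the contradiction: comparing each event's start with the start of the first transfusion is needed only if some recorded events can begin earlier.

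A reader might draw two stronger conclusions that the documents do not support.

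- *That the rule adds events from after the 72-hour window.* The TEAE definition has no upper bound, so a late event is a TEAE with or without a time. The 72-hour limit belongs to a separate reporting period, and the missing-time sentence does not say that it overrides that limit. Handling at that end is unstated; it is not stated to be inclusion.
- *That the safety comparison is diluted by a known amount.* No safety ratio, test or power is planned, the frequency is unknown, and equal misclassification in the two arms would have to be assumed. Unequal completion of forms could shift the comparison either way.

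**Conclusion.** The point holds as a wording defect. Section 8.4.4, read literally, classifies as treatment emergent some events that its own definition excludes, whenever the start is incompletely recorded but the known part places it before the first transfusion. The misclassification can pass into the TEAE, TESAE, UADE, pulmonary, and organ-class and preferred-term tables. Its size in this trial cannot be stated: it depends on whether non-fatal events before the first transfusion are recorded and how often their times are missing, and the answer may be few or none. The primary bleeding endpoint does not use the TEAE flag and is unaffected.

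A related gap is that the SAP does not say how an incomplete date or time is compared with the end of the 72-hour period. It also ties that end to the last on-protocol transfusion in one place and to the final study transfusion in another. Severity: minor.

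**What to change.** Replace the default sentence in section 8.4.4 with wording such as:

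> An AE whose start date or time is missing or incomplete is treatment emergent unless the recorded part of the start date, or an end date earlier than the first transfusion, shows that it began before the first post-randomization PLT transfusion. An AE dated on the day of that transfusion with no time recorded is treatment emergent.

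This keeps the conservative direction wherever timing is truly unknown, and it adds no upper bound to the TEAE definition.

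In addition:

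- State separately how partial dates and missing times are compared with the end of the 72-hour reporting period, and reconcile the two descriptions of the transfusion that starts that clock.
- Report, by arm, the number of TEAEs classified by this default, so that a reader can see whether it matters.

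The cost is a short text change, a small change to the derivation of the TEAE flag, and one count per arm. No new data are needed.

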## 7.13. Treatment Exposure

Exposure to platelet transfusions will be conducted on the mITT set and the SS by reason for transfusion.

One or multiple study platelet transfusions can occur anytime from Study Day 0 to Study Day 27 per subject. If a subject received a platelet unit within four (4) hours of completion of transfusion of the preceding platelet unit, these transfusions will be considered part of a single platelet transfusion episode in analyses.

Additional blood products transfused will be analyzed based on the SS. The number of blood products transfused (other than PTLs), type of blood product transfused, and for RBC transfusions, whether the RBCs were leukocyte-reduced, will be summarized.

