Deaths due to bleeding will be defined by the applicable bleeding grade and reported in the clinical study report. No listings or summaries will be produced as part of this reporting effort.

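### Death due to bleeding is a safety endpoint to be displayed, yet SAP 8.4.4 gives it no listing or summary and defines it by a bleeding grade that does not match it

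*SAP*

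**What the plan says.** The last of the seven safety endpoints in SAP 6.3.2 is bleeding death, worded by cause and covering both a primary and a contributory role. Section 8.4.4 opens with "The following will be displayed" and ends its list with the same item: "Death due to bleeding as the primary or contributory cause of mortality".

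The closing lines of 8.4.4 say something different: "Deaths due to bleeding will be defined by the applicable bleeding grade and reported in the clinical study report". The next sentence is: "No listings or summaries will be produced as part of this reporting effort".

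Just before this, 8.4.4 promises a listing of every death: "All deaths will be listed by treatment group and subject. This listing will include the investigator assessment of cause of death". It also plans a total count of deaths through Day 56.

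Two death windows are given. Adverse event reporting runs, "for deaths including deaths due to bleeding through thirty (30) days following the transfusion end time of the last on-protocol PLT transfusion". The other window is introduced with the words "where the timeframe for reporting death as a safety endpoint of death is through Day 56".

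Bleeding grades come from the daily bleeding assessment coded in Appendix I. The file supplied as the protocol carries the same SAP text on all these points. The Clinical Investigation Plan (CIP) itself is not among the documents.

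**The concern.** There are two problems. First, 8.4.4 tells the programmer both to display bleeding deaths and to produce no listing or summary of them. No other item on the display list is withdrawn in this way.

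Second, the definition changes within the section. The endpoint is a cause of death, but the closing lines turn it into a bleeding grade, without saying which grade or how it relates to the investigator's stated cause.

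This trial tests whether hemostatic efficacy is non-inferior, and a fatal bleed is the most serious way in which hemostasis can fail. The documents give no expected number of such deaths. If they are few, which is an assumption, moving one or two across an unclear definition would change the comparison between arms. Without a prespecified rule and table, the choice of which deaths count would be made after the data are known.

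**Working it through.** **1. The two instructions side by side.** SAP 6.3.2 and the list in 8.4.4 call for a display of bleeding death by cause, primary or contributory. The end of 8.4.4 defines it by grade, reports it in the clinical study report, and rules out listings and summaries. The conflict is one of plain text, and no arithmetic is needed to establish it.

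**2. Grade against cause.** Appendix I derives Grade 4 from five items: B31b, B32c, B33a, B36 and B38.
- B38 is the only one that records a fatal bleed.
- The other four need not be fatal. B33a, for instance, is CNS bleeding on imaging, whether or not there is dysfunction.
- No item at any grade records that bleeding contributed to a death from another main cause.

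Grade 4 as a whole is therefore too broad to identify a bleeding death, and B38 alone does not cover the contributory half of the endpoint.

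**3. When grades are scheduled.** SAP 6.1 plans assessments on Study Days 0 to 27 and at the post-transfusion visit, in some cases Day 28, with a 2-day window. Section 8.1 says that the assessments analyzed, collected on Days 1 to 28, describe bleeding on Days 0 to 27. By the SAP's duration rule in 7.4 (stop − start + 1), this is 27 − 0 + 1 = 28 days, which reproduces the stated maximum of 28. Section 8.1 also lets assessments end at transfusion independence, while 7.7 runs them to the post-transfusion or early termination visit.

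**4. Day 56 window (Days 0 to 56, 57 days).** Days with no scheduled grade:

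| Last day graded | Ungraded days | Count |
|---|---|---|
| Day 29 (full 2-day window used) | 30 to 56 | 56 − 30 + 1 = 27 |
| Day 27 (as scheduled) | 28 to 56 | 56 − 28 + 1 = 29 |
| Day 10 (earliest independence: one transfusion, on Day 0) | 11 to 56 | 56 − 11 + 1 = 46 |

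**5. 30-day window.** SAP 7.13 states: "One or multiple study platelet transfusions can occur anytime from Study Day 0 to Study Day 27 per subject". Let L be the day of the last on-protocol transfusion, from 0 to 27. The window ends on Day L + 30, so between Day 30 and Day 57.
- Graded to Day 27: the window runs 30 − 27 = 3 to 57 − 27 = 30 days beyond the last grade.
- Graded to Day 29: it runs 30 − 29 = 1 to 57 − 29 = 28 days beyond.
- Stopped at independence, with no later off-protocol transfusion: for L up to 17, grading ends on Day L + 10 and the gap is (L + 30) − (L + 10) = 20 days. For L from 18 to 27, grading ends on Day 27 and the gap is L + 3 = 21 to 30 days. Overall it is 20 to 30 days.

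Under every reading, both death windows outlast the scheduled grades.

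**The case against.** The strongest reply is that these deaths do appear in planned output. The clinical study report will cover them, and every death is listed by arm with the investigator's cause. Within the graded period a fatal bleed also enters the by-arm proportion with grade 3 or higher bleeding (SAP 8.2.2, item 3). Serious events are tabulated by organ class and preferred term. This stands: a reader who infers that bleeding deaths would be invisible goes further than the documents allow. None of these outputs isolates the endpoint, however. A listing read by hand after the data are known is not a prespecified count.

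Three other strong readings are tempting and should be resisted.
- A reader might infer that no grade is collected after Day 27. That is wrong: Day 27 is the last bleeding day nominally covered, and the assessment is collected at about Day 28, with 2 days allowed.
- A reader might turn the day counts into a share of bleeding deaths missed. The documents give no timing of deaths, so calendar days cannot be read that way. The choice between two death windows also changes the denominator.
- A reader might infer that late or contributory bleeding deaths are certain to be excluded. Whether B38 can be completed at death, outside the daily schedule, depends on the CIP and the case report form, which are not supplied. The unnamed grade might also be meant more widely than B38.

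It is also fair to say that this is a descriptive safety item. It does not touch the primary inference.

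**Conclusion.** The point holds. The contradiction within 8.4.4 is certain from the text. If its closing lines are followed, a listed safety endpoint of a hemostasis trial has no prespecified by-arm count.

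The mismatch of definition is also real. The grade items do not record a contributory role, four of the five Grade 4 items need not be fatal, and scheduled grading ends before either death window closes. The gap is 27 to 46 days on the Day 56 window. It is 1 to 30 days on the 30-day window across the readings above.

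These counts assume the assessment schedule in SAP 6.1 and 8.1 and no completion of B38 outside it, which cannot be checked here. How many deaths would be affected cannot be estimated from the documents. The matter should be corrected before the final analysis, but it does not bear on alpha, power or sample size.

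**What to change.** Reconcile SAP 6.3.2 and 8.4.4 as follows.

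1. Delete the sentence that rules out listings and summaries.
2. Identify the endpoint from the investigator-assessed cause of death, with bleeding as primary or contributory cause. This matches the endpoint's own wording. First confirm that the form records both roles, since 8.4.4 promises only the investigator's assessment of cause.
3. Keep the bleeding grade as supporting information only, and say whether B38 can be completed outside the daily schedule.
4. Add one table of counts and percentages by arm on the Safety Set, the population that 8.4 sets for all safety endpoints. Show both stated windows: through 30 days after the last on-protocol transfusion, and through Day 56.

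The cost is a few lines of SAP wording, one small table and a check of the cause-of-death field. If that field holds a single cause, the SAP would also need to say, before database lock, how a contributory role is to be established.
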